## Clinical Investigation Plan (CIP)

### 6.2 Investigational device(s) and comparator(s)

Description of the exposure to the investigational device(s)	For each subject, the investigational device (█████ 3D ear scanner) will have an exposure time of approximately 15 minutes, or the length of time it takes to complete a 3D ear scan in its entirety.
Description of the exposure to the comparator(s), if used.	For each subject, the comparator (silicone earmold impression procedure) will occur for approximately 15 minutes, or the length of time it takes to complete a traditional silicone earmold impression.
List of any other medical device to be used during the clinical investigation (if applicable)	N/A
Number of investigational devices to be used, and justification	1 – The investigational device can be reused and sanitized between subjects in accordance with the manufacturer recommendations.

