### 6.3 Participants

Inclusion criteria for participant selection	Adult aged (18+ years) and any degree of hearing loss.
Exclusion criteria for participant selection	External auditory canal must be present and medically unremarkable to facilitate impressions. Participants with surgical ears or without external auditory canals must be excluded.
Criteria and procedures for participant withdrawal or lost to follow up	
During the consent process, participants agree to their involvement being completely voluntary and they may withdraw at any time. A participant is immediately withdrawn if requested to be removed from the investigation. In addition, in the event of an adverse event, the investigation will be paused until the event is reviewed and it is deemed safe to continue the investigation.
 
Attrition will be documented in an excel spreadsheet containing all collected data.
 
In the event of attrition, a rolling recruitment may take place in order to maintain adequate statistical power of the investigation.

Point of enrollment	Following the manufacturer recommended training protocol for the investigatory device for all researcher involved in data collection.
Point of randomization (if applicable).	N/A, conditions will be counterbalanced during enrollment.
Total expected duration of the clinical investigation	Approximately 1 month

SRF-371

Confidential and proprietary.

This document and its contents are confidential and proprietary to Sonova and shall not be reproduced or otherwise disclosed to anyone other than Sonova employees without written authorization from Sonova.

This printout is an uncontrolled copy. The original is stored in the Document Management System  
Template: TPL-368 [2]

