### 6.4 Procedures

#### 6.4.1 Investigation-related Procedure

Three researchers will be facilitating these appointments to limit variability of researcher skill across the two conditions. Researchers will familiarize themselves with the [REDACTED] equipment through independent practice prior to a training facilitated by [REDACTED] (occurring April 23rd) and the researchers will follow [REDACTED] training recommendations (perform scans on 20+ ears following in-person training) prior to data collection. Participants will be seen for one appointment. REUR/REUG, RECD, tympanometry, and reflex thresholds will be collected. The researcher will perform both traditional earmold impressions and 3D ear scans on both ears (conditions will be randomized and counterbalanced across participants). An additional researcher will use a stop watch to quantify the time (mm:ss) it takes for each condition, for both ears. After each procedure, participants and the clinician will also be asked to complete a questionnaire regarding each condition, focusing on their perception of comfort and level of involvement throughout the impression taking. In the event that a clinician feels as though a silicone impression needs to be remade, this will be recorded on the clinician questionnaire. Timing will be recorded for all attempts, but only the time recorded for the final impressions will be used in the data analysis. The resulting data will be compiled for all participants and analyzed using a T-test, to identify any significant differences in the time it takes to complete each method of earmold impressions, in addition to any differences in perceptual comfort.

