## Clinical Investigation Plan (CIP)

- Introduction – “I will be taking some impressions of your ear canals. I will place this foam block in each ear, before filling your canals with the silicone impression material. It will take a few minutes to harden before I remove them. Due to the nature of this study, I am going to ask you to hold any questions until after the procedure is done, but do not hesitate to let me know if you are experiencing any discomfort throughout the procedure.”
- Have materials out and ready to go (impression cartridge in impression gun, box folded together, but do not put a tip on the impression gun)
- Otoscopy
- Cerumen management if needed
- Start timer
- Tie off otoblocks
- Place otoblocks bilaterally
- Confirm otoblock placement with otoscopy
- Put tip on impression gun
- Administer impression material bilaterally
- Check hardness of silicone every 30 seconds
- Remove impressions when set
- Inspect impressions for landmarks
- Perform otoscopy
- Put impressions in box
- End timer
- Administer questionnaires

- Introduction – “I will be using this camera to take some scans of your ear canals. I will place a headset on you and this probe will be inserted into your canal. You will be able to view the procedure on the TV in front of you. Due to the nature of this study, I am going to ask you to hold any questions until after the procedure is done, but do not hesitate to let me know if you are experiencing any discomfort throughout the procedure.”
- Otoscopy
- Start timer
- Sanitize [REDACTED] tip and headset
- Enter patient info
- Hair management
- Headset placement
- Perform scans bilaterally
- Inspect scans for landmarks
- Press power button on screen to save scans
- End timer
- Administer questionnaires

**IN THE EVENT THAT A CLINICIAN FEELS AS THOUGH THE IMPRESSION/SCAN IS UNSATISFACTORY TO SEND IN FOR A CUSTOM PRODUCT, THE PROCEDURE WILL BE REPEATED. THE TIMING OF ALL PROCEDURES WILL BE RECORDED ON THE TIMING**

SRF-371

SKP-371

Confidential and proprietary.  
This document and its contents are confidential and proprietary to Sonova and shall not be reproduced or otherwise disclosed to anyone other than Sonova employees without written authorization from Sonova.

This printout is an uncontrolled copy. The original is stored in the Document Management System.  
Template: TPL-368 [2]

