# Clinical Investigation Plan (CIP)

## RECORDS, AND REASON FOR REPEAT WILL BE CAPTURED IN THE CLINICIAN QUESTIONNAIRE.

These timing details do not include setting up equipment (removing from drawers/cabinets, etc.), sending a silicone impression order through the eStore, or sending [REDACTED] scans to a manufacturer. One researcher ([name]) will take a one-time time recording of these processes and others that may be of interest, separate from data collection.

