#### 7.3.1 Datasets to be analyzed, analysis population

Total procedure time will be recorded in seconds. Each procedure time will be recorded along with the audiologist, the anonymous participant ID, the procedure methodology (i.e., scanning or traditional silicone impressions), and the ordinal number of the procedure for the given methodology by the respective audiologist. Qualitative data will be collected as a question, response, methodology, and anonymous participant ID.

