## 8 Quality Assurance and Control

### 8.1 Data Handling and record keeping/ archiving

Study data is recorded both with paper and with electronic Case Report Forms (p/eCRF). For each enrolled study participant a CRF is maintained. All CRFs are kept current to reflect the subject's status at each phase during the course of study. Participants cannot be identified in the CRF by name or initials and birth date but an appropriate coded identification is used. All study team members are authorized for the CRF entries and it is assured that any authorized person can be identified both for pCRFs and eCRFs. If pCRFs are used, the investigator's acronym as well as the subject ID is filled in and data are entered into an electronic file for analysis by the respective investigator and data get monitored by the assigned monitor. In case of a self-evident corrections, either the subject does it by himself or the investigator undertakes the correction by crossing out the word/sentence with a single horizontal line and by adding the correction including his personal identifier and the date.

SRF-371

Confidential and proprietary.

This document and its contents are confidential and proprietary to Sonova and shall not be reproduced or otherwise disclosed to anyone other than Sonova employees without written authorization from Sonova.

This printout is an uncontrolled copy. The original is stored in the Document Management System  
Template: TPL-368 [2]

Page 18/26

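### Cerumen is managed before silicone impressions but not before scans, so for a participant who needs removal the canal state at the scan depends on which method comes first

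*Combined protocol and SAP*

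**What the plan says.** Section 6.4.1 gives a step list for each method, which also defines when the clock runs. The silicone list starts with an introduction, preparation of materials and otoscopy, then "Cerumen management if needed", and only then starts the timer. The second list has no visible title, but its patient script ("I will be using this camera to take some scans of your ear canals") identifies it as the scan list. It goes from introduction to otoscopy to the timer, with no cerumen step. Nothing in the visible text suggests that such a step was blacked out. Cerumen is mentioned nowhere else in the document.

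The same section has each participant attend once and undergo both methods on both ears; "conditions will be randomized and counterbalanced across participants". Section 6.3 limits entry by anatomy: "External auditory canal must be present and medically unremarkable to facilitate impressions". The primary model in section 7.3.2 has a fixed effect of method and a random effect of audiologist, with no term for order.

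**The concern.** Procedure time is the primary endpoint, and scan time is one half of the comparison. In a within-participant design the two methods should meet the same ear in the same state, or any difference in state should be a deliberate part of the method. Here the canal may be cleared partway through the visit, and whether that happens before or after the scan is decided by the order assignment. Mean scan time would then average two canal states among participants with wax, and the plan does not say which state is meant. The silicone times have no such mixture.

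**Working it through.** The plan states no figure on this point, so there is nothing to reproduce. The check compares the two lists and then asks what counterbalancing does.

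**Canal state for a participant who needs removal, with the lists followed as written**

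| Order | State at scan | State at silicone |
|---|---|---|
| Silicone first | cleared | cleared |
| Scan first | uncleared | cleared |

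**Why counterbalancing does not cancel it.** Let S be the scan time in a cleared canal, M the silicone time, and d the change in scan time when the canal is uncleared (positive, negative or zero).

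- An ordinary order effect c, which changes the second procedure by the same amount whichever method it is, gives scan minus silicone of S − (M + c) when the scan is first and (S + c) − M when silicone is first. The average is S − M, so c cancels.
- The cerumen effect gives (S + d) − M when the scan is first and S − M when silicone is first. The average is S − M + d/2, so half of d remains.

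With an even split of orders, a simple order term in the model would not help. The estimate would still be the average of the two order-specific differences.

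**Size, as illustration only.** If a share p of participants needs removal and half are scanned first, the shift in mean scan time is 0.5 × p × d.

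- From the documents: 30 participants (synopsis and section 6.1.1), and a scan that "will have an exposure time of approximately 15 minutes" (section 6.2), that is 900 s.
- Assumed: an even split, 30/2 = 15 scanned first; p from 0 to 33%; d from 0 to 120 s in either direction.
- Scan-first participants affected: 15 × 0 = 0 to 15 × 0.33 = 4.95, about 5.
- Shift: 0 s to 0.5 × 0.33 × 120 = 19.8 s. A middle case of p = 10% and d = 60 s gives 0.5 × 0.10 × 60 = 3.0 s.
- Relative to 900 s: 0 to 19.8/900 = 2.2%; middle case 3.0/900 = 0.33%.
- The synopsis speaks of a time variance of about 5 minutes. If that is read as the standard deviation of paired differences (a further assumption), the standard error is 300/√30 = 54.8 s. The shift is then 0 to 19.8/54.8 = 0.36 of one standard error; middle case 3.0/54.8 = 0.05.

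These figures measure the shift from a cleared canal in both orders. If the uncleared canal were the intended state, the shift would have the same size and the opposite sign.

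**After the fix.** With removal done before either method, no scan takes place in an uncleared canal and the order-dependent term is 0.

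**The case against.** **The strict reading is not compelled.** Otoscopy precedes the timer in both lists, the operators are licensed audiologists, and nothing forbids clearing the canal before a scan. Section 6.4.1 also collects real-ear and tympanometric measures in the same visit, which might prompt earlier removal. This stands as a reason to expect few affected scans. But no text directs clearing before a scan, the timing of those measures against the two methods is not fixed, and three audiologists could each decide differently.

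**Eligibility may leave almost no one affected.** That is possible. The criterion does not name cerumen, however, and the silicone list itself provides for removal in enrolled participants.

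**The asymmetry may be real workflow.** Removal may be needed for silicone and not for scanning, and the manufacturer's training recommendations are not available to settle this. This is the strongest point, because it means that a cleared canal is not obviously the right reference. It does not remove the inconsistency: silicone-first participants are still scanned in a canal that scanning alone would not have required to be cleared.

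**Repeats absorb some of it.** An unsatisfactory scan is repeated, and section 6.4.1 analyses only the final time (its wording speaks of impressions), so time lost to a failed scan may drop out. A slow but acceptable scan triggers no repeat.

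**Stronger readings that the documents do not support.** A reader might infer that the scan times are biased in a known direction; no text says that wax lengthens or shortens a scan. A reader might infer that removal inflates the silicone time; it takes place before the timer starts. A reader might also infer that order and canal state will go unrecorded. Section 7.3.1 lists analysis fields, including "the ordinal number of the procedure for the given methodology by the respective audiologist", which counts procedures within one method and so does not give the order within a participant. But that list is not every record kept: "For each enrolled study participant a CRF is maintained" (section 8.1), and for repeats "REASON FOR REPEAT WILL BE CAPTURED IN THE CLINICIAN QUESTIONNAIRE" (section 6.4.1).

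**Conclusion.** The point holds as a cheap improvement to the procedure, not as an error that undermines the result. The two lists differ, and followed as written they make canal state at the scan depend on order for anyone who needs removal. Neither counterbalancing nor the primary model removes this. How many participants are affected, and whether scan time changes at all, cannot be known from the documents. The 0 to 19.8 s range rests wholly on assumed shares, assumed changes and an assumed even split, and its upper end multiplies two assumed extremes. The direction is unknown and the effect may be zero. The study is exploratory and sets no effect size to confirm (sections 5.3 and 7.1), so no conclusion is shown to change.

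**What to change.** Place otoscopy and any needed cerumen management once, untimed, ahead of the first procedure in both orders, and take the cerumen step out of the silicone list. Every scan and every impression then starts from the same canal state.

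The cost is one moved step, with no extra visit, participant or analysis. No method-order field is needed in the analysis dataset on this account, because once the canal is cleared before both methods the field has no use for this purpose. There is one real downside: in participants with wax, scan times will always describe a cleared canal. If the scanner does not need one, that is slightly less representative of clinic workflow, and the report should say so.

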# Clinical Investigation Plan (CIP)

## RECORDS, AND REASON FOR REPEAT WILL BE CAPTURED IN THE CLINICIAN QUESTIONNAIRE.

These timing details do not include setting up equipment (removing from drawers/cabinets, etc.), sending a silicone impression order through the eStore, or sending [REDACTED] scans to a manufacturer. One researcher ([name]) will take a one-time time recording of these processes and others that may be of interest, separate from data collection.

### 6.4.2 Sponsor activities

N/A

### 6.4.3 Outcome comprising factors

Inclusion/exclusion criteria, limiting bias with multiple researchers, uncertainty of how HL may influence subjective preferences, etc.

Exclusion criteria has been designed to limit comprising factors due to participant anatomy. Multiple researchers will be administering appointments to limit researcher bias.

## 6.5 Monitoring plan

The extent and nature of monitoring appropriate for the clinical investigation including the strategy for source data verification (SDV) are based on considerations such as the objective, design, complexity, size critical data points and endpoints of the clinical investigation. A detailed plan for monitoring arrangements is provided separately from this CIP (TPL-160).

# 7 Statistical design and analysis

The description of and justification for the statistical design and analysis of this clinical investigation is in line with Chapters 5 and 6.

### 7.1 Determination of Sample Size

A priori sample size estimation was not performed for this investigation, as the investigation is exploratory and does not aim to confirm any effect with statistical significance and power.

### 7.2 Statistical criteria of termination of trial

This is an exploratory trial and will not have statistical criteria for termination.

### 7.3 Planned Analyses

The statistical analysis plan includes the methods and types of the analysis, the variables the data sets and the timeframe when the (interim) analysis is planned.

#### 7.3.1 Datasets to be analyzed, analysis population

Total procedure time will be recorded in seconds. Each procedure time will be recorded along with the audiologist, the anonymous participant ID, the procedure methodology (i.e., scanning or traditional silicone impressions), and the ordinal number of the procedure for the given methodology by the respective audiologist. Qualitative data will be collected as a question, response, methodology, and anonymous participant ID.

#### 7.3.2 Primary Analysis

Analysis of procedure time data will take place at the conclusion of the trial. The intended analysis assumes a normally-distributed response variable. As such, procedure times for

SRF-371

Confidential and proprietary.

This document and its contents are confidential and proprietary to Sonova and shall not be reproduced or otherwise disclosed to anyone other than Sonova employees without written authorization from Sonova.

This printout is an uncontrolled copy. The original is stored in the Document Management System  
Template: TPL-368 [2]

## Clinical Investigation Plan (CIP)

each methodology will be tested for normality using a Shapiro-Wilk test. If the data are normally distributed, additional analysis will proceed immediately. If data are not normally distributed, transformation(s) may be performed on the data, as appropriate, to achieve an approximately normal distribution of the response data for further analysis.

Data (raw or transformed, per above) will then be subjected to analysis via linear mixed effects modeling. The model will be constructed to regress (raw or transformed) procedure time on a dummy variable of methodology (fixed effect), with a random effect of audiologist. This model will allow the investigators to evaluate the relative difference in procedure time between the methodologies, while removing and separately evaluating the variance contributed by the audiologist undertaking the procedure.

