## Clinical Investigation Plan (CIP)

	Number of Arms: [2]		
	 Observational Study		
	Investigation Model		Time Perspective
	 Cohort	 Ecologic	 Retrospective
	 Case-Control	 Family-based	 Prospective
	 Case-only	 other:	 Cross-sectional
	 Case-crossover		 other:
	Number of Groups/ Cohorts: [1]		
Type of design	 Exploratory	 Confirmatory	 Observational
Inclusion / Exclusion criteria:	External auditory canal must be present and medically unremarkable to facilitate impressions. Participants with surgical ears or without external auditory canals must be excluded.		
Measurements and procedures:	Three researchers will be facilitating these appointments to limit variability of researcher skill across the two conditions. Researchers will familiarize themselves with the [REDACTED] equipment through independent practice prior to a training facilitated by [REDACTED] (occurring April 22nd) and will follow [REDACTED] training recommendations (perform scans on 10+ ears following in-person training) prior to data collection. Participants will be seen for one appointment. The researcher will perform both traditional earmold impressions and 3D ear scans on both ears (conditions will be randomized and counterbalanced across participants). An additional researcher will use a stop watch to quantify the time (mm:ss) it takes for each condition, for both ears. At the end of the appointment, participants will also be asked to complete a subjective questionnaire regarding each condition, focusing on their perception of comfort and level of involvement throughout the impression taking. The resulting data will be compiled for all participants and analyzed using a T-test, to identify any significant differences in the time it takes to complete each method of earmold impressions, in addition to any differences in subjective domains.		
Intervention:	[REDACTED] 3D Ear Scanning Solution		
Control Intervention (if applicable):	Traditional silicone earmold impression material, administered by a cartridge impression gun.		

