Number of Participants with Rationale:	N = 30 (10 participants per researcher). Both conditions will be measured for each participant. This sample population will provide an adequately powered study under the assumption that time variance of each condition is within approximately 5 minutes.		

SRF-371

Confidential and proprietary.

This document and its contents are confidential and proprietary to Sonova and shall not be reproduced or otherwise disclosed to anyone other than Sonova employees without written authorization from Sonova.

This printout is an uncontrolled copy. The original is stored in the Document Management System  
Template: TPL-368 [2]

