#### 5.2 Primary and Secondary Objectives

The Primary objective is to identify any significant differences in the time required for a provider to complete the workflow of an [REDACTED] 3D ear scanner, compared to traditional silicone earmold impression procedures. The secondary objective is to identify any significant preferences for both providers and patients.

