## 7.4 Handling of missing data and drop-outs

Participants with missing procedure time data for either or both methodologies will be excluded from statistical analysis entirely. Missing qualitative data will not impact statistical analysis (as no statistical analysis is planned for qualitative data). Drop-outs will not be replaced during this study. Achieved statistical power will be calculated and documented if the planned sample size is not achieved.

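### The primary model in 7.3.2 ignores that each participant is measured under both methods, so its standard error is right only if a participant's two times are uncorrelated; 1.3 and 6.4.1 name an unspecified T-test instead

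*Combined protocol and SAP*

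**What the plan says.** Section 1.3 plans 30 participants, 10 per researcher, and states: "Both conditions will be measured for each participant". Section 6.4.1 has the researcher carry out both methods on both ears of a participant, so participants are nested within audiologist. Section 7.3.1 records participant ID. Section 7.4 keeps only complete pairs: "Participants with missing procedure time data for either or both methodologies will be excluded from statistical analysis entirely".

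The primary analysis in 7.3.2 regresses "procedure time on a dummy variable of methodology (fixed effect), with a random effect of audiologist". The stated purpose of the random effect is "removing and separately evaluating the variance contributed by the audiologist undertaking the procedure". No section adds a participant effect, a repeated-measures covariance or an order term.

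Sections 1.3 and 6.4.1 both say something else: "The resulting data will be compiled for all participants and analyzed using a T-test". Neither says whether the test is paired. In both places the same sentence extends the test to questionnaire domains, whereas 7.3.3 and 7.4 say questionnaire data will not be analysed statistically.

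Order of methods is counterbalanced (6.1.1), but the dataset in 7.3.1 holds only "the ordinal number of the procedure for the given methodology by the respective audiologist". That is a running count per audiologist and method. It does not show which method came first in a given participant.

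**The concern.** The design produces 30 pairs, but the model treats the 60 times as independent given the audiologist. The audiologist effect absorbs only what all participants of one audiologist share. It leaves rho, the remaining correlation between one participant's two times.

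The documents give no value for rho. Varied canal sizes and shapes (6.3) could make it positive. Silicone setting is timed in one workflow only (6.4.1, timing details), which could keep rho low and make the two SDs unequal.

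What is at stake is the SE, interval and p-value for the primary objective, which is to "identify any significant differences in the time required for a provider to complete the workflow". The T-test wording adds to this: the same objective has up to three candidate analyses (mixed model, unpaired t, paired t), and their SEs differ.

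**Working it through.** **Inputs from the documents.** 3 audiologists x 10 participants x 2 methods (1.3, 6.4.1); methodology fixed and audiologist random (7.3.2); complete pairs (7.4). For variability, the sample size holds "under the assumption that time variance of each condition is within approximately 5 minutes", which can be read as an SD of 5 min or a variance of 5 min^2 (SD 2.24 min).

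**Assumptions.** Two-sided alpha 0.05; rho from -0.2 to 0.7; audiologist SD 2 min; order balanced within audiologist; differences of 1.0 to 2.5 min.

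**The plan's own figure.** N = 30 cannot be reproduced. No alpha, power target or effect size is given, and 7.1 says that no a priori estimation was done.

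**Step 1: standard errors.** With equal SDs sigma in this balanced layout:

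- True SE of the mean difference = sqrt(2 sigma^2 (1 - rho) / 30).
- Planned SE = sqrt(2 MSE / 30), with E[MSE] = sigma^2 [(1 - rho) + (54/56) rho], which is close to sigma^2.
- Ratio, planned to true: about 1/sqrt(1 - rho).

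Example, sigma = 5 and rho = 0.5: true SE = sqrt(2 x 25 x 0.5 / 30) = 0.91. E[MSE] = 25 x (0.5 + 0.482) = 24.6, so planned SE = sqrt(2 x 24.6 / 30) = 1.28 (mean 1.27 in simulation). The ratio is 1.40.

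**Step 2: ratio and type I error** (simulation, at least 40,000 trials per setting, equal SDs, no audiologist-by-method difference):

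| rho | planned SE / true SE | type I error, planned | type I error, paired |
|---|---|---|---|
| -0.2 | 0.91 | 7% | 5% |
| 0 | 1.00 | 5% | 5% |
| 0.3 | 1.19 | 2% | 5% |
| 0.5 | 1.40 | 0.7% | 5% |
| 0.7 | 1.8 | 0.1% | 5% |

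With SDs in ratio k, the approximate ratio is 1/sqrt(1 - 2k rho/(1 + k^2)). At rho 0.3, 0.5 and 0.7 this gives 1.15, 1.29 and 1.51 for k = 2, and 1.10, 1.20 and 1.31 for k = 3. Unequal SDs reduce the error but do not remove it.

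**Step 3: power at rho 0.5, under both readings of the 5 minutes:**

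| reading | difference | planned | paired |
|---|---|---|---|
| SD 5 min | 2.5 min | 48% | 75% |
| variance 5 min^2 | 2.0 min | 98% | 99.7% |
| variance 5 min^2 | 1.0 min | 37% | 66% |

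With SD 5 min, the T-test of 1.3 and 6.4.1 has 42% power for 2.5 min if unpaired and 75% if paired. The 95% interval half-width is 2.5 to 2.6 min as planned, against 2.6, 2.2, 1.9 and 1.4 min paired at rho 0, 0.3, 0.5 and 0.7.

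**Step 4: audiologist-by-method differences.** Suppose the method difference varies between audiologists with an assumed SD of 1 or 2 min, audiologists are treated as a random sample, rho is 0.5 and the SD is 5 min. The planned model then rejects about 2% or 8% of null trials. Differences adjusted for order reject about 9% or 19%. Conditional on the three audiologists, the difference analysis holds about 5% once audiologist is a term in it.

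**Step 5: which repair works.** At rho -0.2 a random participant intercept is estimated as zero in about 86% of trials, and type I error stays at about 7%. Within-participant differences hold 5%. For clearly positive rho the two give the same SE: 0.90 for both at rho 0.5.

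**The case against.** The study is labelled exploratory. Section 7.1 disclaims any aim of confirming an effect with significance and power, and no effect size is set. The estimate is unbiased, and rho is unknown and may be low. All of this stands, and it limits the weight. It does not dispose of the point: the objective is still worded in terms of significant differences, 1.3 claims adequate power, 7.4 plans to report achieved power if the sample falls short, and an exploratory estimate still needs a correct interval.

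A reader might infer more than the documents support, in four ways.

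- *That the plan inflates false positives.* With no audiologist-by-method difference this needs negative rho, the less plausible direction.
- *That the planned test is always safe for positive rho.* It is conservative only while the method difference is similar across audiologists; step 4 shows about 8% at an assumed SD of 2 min.
- *That a large power loss is established.* The fall from 75% to 48% belongs to one reading of the 5 minutes. Under the other reading the loss at 2.0 min nearly vanishes and reappears only for smaller differences.
- *That pairing supports conclusions about an average provider (6.1.2).* It does not. Treated as sampling from providers, the narrower SE rejects too often.

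A fair objection to using differences is that they remove the audiologist main effect, which 7.3.2 wants to evaluate. A participant term added to the existing model is the smaller repair for rho of zero or above.

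**Conclusion.** The point holds on the text. The design is paired, the primary model does not use the pairing, and two other sections name a different and incompletely specified test. The estimate of the difference is sound; the SE, interval and p-value are correct only at rho = 0. For rho between 0.3 and 0.7, equal SDs and no audiologist-by-method difference, the SE is about 1.2 to 1.8 times too large, and by less if the SDs differ. At rho -0.2 it is about 9% too small.

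The mismatch and the conflict between sections are certain. Their size is not, because it rests on an undocumented rho and an ambiguous variability statement. For an exploratory study the main consequence is lost precision and an incorrect interval. It should be corrected before analysis, but it does not undermine the design.

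**What to change.** 1. In 7.3.2, use the pairing in one of two ways: (a) add a random intercept for participant within audiologist to the stated model, which keeps the audiologist variance component and is valid for rho of zero or above; or (b) analyse within-participant differences (scan minus silicone) with order and audiologist (centred fixed factor) as terms, which is valid for either sign of rho. Under (b), report mean time by audiologist and method separately.
2. In 7.3.1, add a column for which method came first in each participant. Check normality on the residuals or differences, not on the times by method.
3. In 1.3 and 6.4.1, replace the T-test for procedure time only with this same analysis. Delete the T-test for subjective domains and comfort, to agree with 7.3.3 and 7.4.
4. Report the method difference for each audiologist, and state that with three audiologists neither form supports inference to the average provider of 6.1.2.

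Cost: wording in four sections and one data column, with no extra participants or procedures. The downside is the explicit limit on inference, because the narrower SE does not cover audiologist-by-method variation. Estimates per audiologist will be imprecise: a 95% half-width of about 3.8 min at rho 0.3 and 3.3 min at rho 0.5, with SD 5 min and 10 participants each.
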